### **Recruitment**

Non-probability (convenience) sampling will be used to recruit participants within the greater San Diego area via a variety of methods, including through FHCSO outreach and HIV/STI testing programs, a Spanish language Latino MSM support group, gay-friendly events, such as Pride, and flyering local LGBT community centers, gay-identified/friendly coffee shops, gyms, and bars. We will also utilize online recruitment methods, including targeted ads through Facebook and Instagram, and use of geolocation social networking mobile applications tailored to sexual minority men (e.g., Grindr, Scruff, Jack’d). Potential participants recruited using flyering or targeted ads will be requested to contact study personnel via email or telephone. A bilingual member of the study team will contact each potential participant via telephone to explain the study and screen for inclusion. The bilingual research assistants will be native Spanish speakers who are bilingual in English and Spanish; they will have some university education and research experience. If a potential participant screens positively for the study, an in-person baseline visit will be scheduled, in which the inclusion/exclusion criteria will be assessed in further detail. Reasons for non-participation of potential participants will be documented.

### **Randomization**

The research coordinator will use the Randomizer for Clinical Trial computer application to randomize each participant to either UC or PN via an iPad immediately following the baseline survey data collection. Randomizer for Clinical Trial will implement a blocked randomization sequence (in blocks of 4 participants) to balance randomization across the arms of the study. The randomization sequence will be concealed from all members of the study team prior to randomization.

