Developing a Patient Navigation Intervention for PrEP Continuum of Care Among Young Latino MSM  
(PrEParate)  
Study Protocol and Statistical Analysis Plan  
NCT04048382  
August 2, 2019

Using a randomized controlled trial design, a pilot test of the PN intervention will be conducted in collaboration with the Family Health Centers of San Diego (FHCS), a federally qualified health center. Bilingual research assistants will recruit 60 young adult Latino MSM at-risk for HIV in San Diego County, California; this sample size is well within the bounds of recommendations for pilot trials. After a research assistant obtains informed consent, participants will complete baseline surveys, and then the research assistant will individually randomize each participant to 1 of 2 conditions: usual care plus written information (UC) or PN. At 3- and 6-month follow-up, participants will be asked to complete surveys. Individuals randomized to PN will also be asked to participate in a key informant interview at 6-months. Participants' electronic health records (EHR) will be reviewed at 6-month follow-up to assess their engagement in the PrEP continuum. The study methods and PN intervention will be reviewed for feasibility and acceptability, as well as preliminary impact of the PN intervention in preparation for a future full-scale efficacy trial. In addition, the pilot test will evaluate preliminary impact on seven PrEP continuum-related primary outcomes (i.e., scheduled and attended PrEP consultation; PrEP prescription received; PrEP prescription filled; PrEP initiated; self-reported PrEP adherence; and PrEP follow-up medical appointment attended). Analyses will be performed under the intent-to-treat (ITT) principle. Participants will be compensated with a \$50 gift card to an online retailer at each of the three assessment time points (baseline, 3-month follow-up, 6-month follow-up). (See Appendices 1-3 for informed consents and WHO Trial Registration Data Set)

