### **Usual Care Intervention**

Immediately following randomization, the research team member will provide participants randomized to UC the CDC’s 2-page *PrEP Information Sheet* in the participant’s preferred language (either English or Spanish). This 2-page booklet includes the following information: 1) overview of PrEP; 2) eligibility for PrEP; 3) efficacy of PrEP; 4) safety of PrEP; and 5) obtaining, initiating, and adhering to PrEP. Participants will also be provided with both verbal and written information regarding available sexual health and HIV prevention services, including PrEP, at FHCSO. Comprehensive HIV-prevention healthcare, including PrEP, is available to study participants at FHCSO at no or minimal cost.

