Following patient randomization, the research coordinator will notify the patient navigators regarding the patient's assignment to PN. A patient navigator will contact the participant to schedule the first in-person meeting at a time and location of the participant's convenience. The navigators will provide services to patients using PN intervention manuals and materials the team has developed (see Figure 1 for examples of PN services provided at each level of PrEP continuum). Services will generally focus on: 1) overcoming community, health system, interpersonal, and individual barriers to accessing PrEP-related healthcare; 2) increasing each patient's knowledge, attitudes, and self-efficacy for initiating and adhering to PrEP; 3) improving communication between the patient and healthcare team through appointment scheduling and reminders; and 4) sexual risk reduction counseling. PNs do not meet participants at their homes but at any safe location to conduct the intervention (e.g., private rooms in a library, clinic, or community outreach center). Meeting locations are coordinated between the participants and the PNs. PNs communicate with participants via text, phone call, and videoconferencing, based on the participant's preference.

The FHCSO HIV Services Program Manager will provide day-to-day supervision of the patient navigators and will meet with each navigator weekly and document successes and challenges to PN intervention implementation through a weekly written report. The study staff also provide weekly supervision and will rate patient navigators' delivery of the intervention, via audio recordings, using an intervention fidelity monitoring form.

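### Fixed blocks of 4, with the size not withheld from staff who see assignments, make on average one third of allocations certain in advance for one person tracking them all; varying, undisclosed sizes are a cheap optional improvement

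*Combined protocol and SAP*

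**What the plan says.** The Randomization section gives one block size: the application will "implement a blocked randomization sequence (in blocks of 4 participants) to balance randomization across the arms of the study". It then adds "The randomization sequence will be concealed from all members of the study team prior to randomization". That protection covers the sequence. Nothing in the documents extends it to the block size, which anyone holding the protocol can read.

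The staff around randomisation learn the assignments:

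- Randomization: "The research coordinator will use the Randomizer for Clinical Trial computer application to randomize each participant".
- PN Intervention: after randomisation, "the research coordinator will notify the patient navigators" of assignments to PN.
- Usual Care Intervention: "Immediately following randomization, the research team member will provide participants randomized to UC" their written material.

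The Statistical Analysis Plan states blinding only for the biostatistician. The documents give no numerical allocation ratio and describe no stratification.

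They also differ on who randomises. The opening overview says "the research assistant will individually randomize each participant to 1 of 2 conditions", whereas the Randomization section names the research coordinator.

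**The concern.** Hiding the list does not stop someone from deducing the end of a block from the assignments already made. In a block of 4 with two places per arm, the fourth allocation always follows from the first three, and the third follows whenever the first two match. A person who knows the size and has seen the earlier assignments therefore knows some allocations before the participant is randomised.

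What is at stake is selection before randomisation. Consent and the baseline survey come first, so foreknowledge could act only through telephone screening, scheduling or the conduct of the baseline visit. The inclusion criteria admit current and past PrEP users, so who is enrolled into which arm bears on the PrEP continuum outcomes. Intention-to-treat analysis does not repair selection that happens before assignment. The pilot is also meant to prepare a full-size trial and reviews its own randomisation process, so a weakness left here could carry forward.

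**Working it through.** The plan gives no predictability figure, so there is none to reproduce.

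**Inputs.** Two arms and 60 participants (opening overview); block size 4 (Randomization), hence 60/4 = 15 blocks. Assumed: 1:1 allocation, inferred from the stated aim of balance, and a single unstratified list.

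**One person who knows the size and tracks everything.** A 2+2 block has 6 orderings. In AABB and BBAA the third and fourth allocations are certain (2 each); in the other four only the fourth is (1 each).

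- Certain per block: (2×2 + 4×1)/6 = 8/6 = 1.333, a share of 1.333/4 = 1/3.
- Over 15 blocks the count is 15 + Binomial(15, 1/3). The mean is 15 + 5 = 20 of 60, the SD √(15 × 1/3 × 2/3) = 1.83, and the 95% range 17 to 24.
- Minimum 15, maximum 30 of 60; the probability of more than 20 is 0.38.
- Best-guess accuracy by position is 1/2, 2/3, 2/3 and 1, so (17/6)/4 = 17/24 = 71%.

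**Several people who do not share results.** Let person i make a share qᵢ of the randomisations, know the position in the block, and see only their own assignments. An allocation is certain to that person if they made both assignments of the pair that has used up one arm. Such a pair exists with probability 1/3 before position 3 and always before position 4. The certain share is therefore (1/4)(1/3 + 1) Σqᵢ³ = (1/3) Σqᵢ³.

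| Who randomises | Σqᵢ³ | Certain share | Of 60 |
|---|---|---|---|
| One person | 1 | 33.3% | 20 |
| Two, 90/10 | 0.730 | 24.3% | 14.6 |
| Two, 80/20 | 0.520 | 17.3% | 10.4 |
| Two, 50/50 | 0.250 | 8.3% | 5.0 |
| Three, equal | 0.111 | 3.7% | 2.2 |

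**Sizes varied between 4 and 6 (illustrative, equal probability).** The tracker knows the set of sizes but not the size of each block. In 10,000 simulated lists of 60, 5.6% of allocations are certain (about 3 of 60). Those predictable with probability at least 0.9 fall from 33% to 9%. Best-guess accuracy is 69%. Someone who knows no block size, always guesses the arm that is behind and tosses a coin when the arms are level, scores 71% with fixed 4 and 69% with varied sizes.

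**Balance at 60 with sizes 4 and 6.** The mean size is 5. In the long run an even position is a block boundary with probability 2/5 = 0.4. It falls two places into a 4-block, two places into a 6-block, or four places into a 6-block with probability 0.2 each. The chance of being two apart is 1/3 in the first of these cases and 2/5 in each of the other two. So P(31/29) = 0.2×1/3 + 0.2×2/5 + 0.2×2/5 = 0.2267, which agrees with the exact calculation at 60. Otherwise the split is 30/30; nothing worse is possible.

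**The case against.** The strongest reply is that the plan contains no error here. Allocation is made by an application straight after baseline data collection, the sequence is concealed from the whole team, and a fixed block of 4 guarantees 30/30 under 1:1. Silence about the block size is not evidence that anyone works out allocations. All of this stands, and it is why the point is an improvement rather than a correction.

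The route to harm is also narrow. Under Recruitment, "A bilingual member of the study team will contact each potential participant via telephone to explain the study and screen for inclusion"; that person may not be the one who randomises. Before randomisation, the documents place the recording of PrEP status only at the baseline visit, after scheduling, and the survey follows consent. "Reasons for non-participation of potential participants will be documented", and the Feasibility Evaluation reviews recruitment and difficulties with randomisation. These steps would make selective enrolment easier to see but would not prevent prediction.

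The benefit is modest too: ordinary guessing barely changes (71% to 69%). What is removed is most of the certainty, which is the part that concealment is meant to prevent.

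A reader might infer that enrolment will be biased. The documents do not support that: they do not show that anyone would act on a prediction, and they give nothing from which to size a bias.

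**Conclusion.** The point holds as an avoidable weakness in concealment. One stated block size, not withheld from staff who see assignments, makes on average 20 of 60 allocations certain in advance. This assumes 1:1 allocation, one unstratified list, and one person who knows the size and tracks every assignment. With several randomisers who do not share results the figure falls, to 5.0 of 60 for two equal sharers. The documents do not settle which case applies, because they name two different roles as the randomiser.

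A reader might take one third as a ceiling. It is the mean under the least favourable staffing; the count can reach 30 of 60 and exceeds 20 with probability 0.38. A reader might also conclude that the sequence itself is exposed. It is not: the plan conceals it, and the weakness lies only in what can be deduced from past assignments.

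The SAP treats the analyses as exploratory and not powered for efficacy, so the change is worthwhile but optional in this pilot.

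**What to change.** In the Randomization section, replace the parenthesis giving the block size with: *randomly varying block sizes, generated within the application; the sizes are not disclosed to staff who enrol or randomise until enrolment closes*. Record the sizes, for example 4 and 6, outside the protocol text.

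If the application cannot vary sizes, at least withhold the block size from those staff. This is weaker, since guessing the arm that is behind still succeeds 71% of the time. Do not substitute a list held by staff: it would conflict with the section's own concealment of the sequence from every team member.

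Separately, reconcile the opening overview with the Randomization section on who randomises.

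The cost is one sentence, a settings change that the documents do not show the application to support, and with sizes 4 and 6 a 31/29 instead of a 30/30 split with probability about 23%.

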### **Inclusion/Exclusion Criteria**

The following criteria are required for study inclusion: 1) age 18 to 29 years; 2) identifies as male; 3) identifies as gay/bisexual or reports having sex with men in past 12 months; 4) identifies as Latino/Hispanic; 5) self-reports being HIV-uninfected; 6) resides in San Diego County, California; 7) speaks English or Spanish; 8) is willing and able to provide informed consent; and 9) reports at least one HIV risk factor as informed by Centers for Disease Control and Prevention (CDC) guidelines. MSM are at elevated risk for HIV if they report one of the following: 1) an HIV-positive sexual partner; 2) diagnosis of a bacterial sexually transmitted infection (STI) within the past 12 months; 3) engaging in

condomless anal sex with a non-monogamous partner in the past 12 months; 4) engaging in commercial sex work in the past 12 months; 5) injection of illicit drugs and sharing of injection equipment in the past 12 months; or 6) engaging in drug treatment for injection drug use in the past 12 months. Individuals will be excluded if they self-report being HIV-positive. The intervention is designed to meet the needs of MSM who self-report their gender identity as male, but other gender identities are allowed in the study. If a potential participant indicates that their gender identity is not “male” (e.g., transgender, non-binary, gender fluid), then the participant will be informed that the study was designed for cis-male MSM; and will then be invited to determine whether they feel that they will benefit from the study based on their gender identity. Participants who previously were prescribed or are currently taking PrEP will be included in the study. Participants are not required to seek care at FHCSO to be included in the study.

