Sexual Behaviors	3 items measuring over the past 3 months the total number of male anal sex partners, number of partners in which condoms were not used exclusively, and the HIV status of partners. Data are collected using numeric text entries.		X	X	X	
Mental health	21 item Depression, Anxiety, Stress Scale (DASS-21) measuring depression, anxiety, and stress over the past week. Data are collected using a Likert scale.	Lovibond & Lovibond, 1995	X	X	X	
Substance use	15 items measuring drug, alcohol, and tobacco use over the past month. Data are collected using a Likert scale.	Team developed	X	X	X	
Social support	8-item PROMIS Informational and 7-item Emotional Support Scales, respectively, measuring perceived sources of support over the past month. Data are collected using a Likert scale.	Hahn et al., 2014	X	X	X	
Patient Satisfaction with PrEP-related services	8-item Client Satisfaction Questionnaire (CSQ-8) measuring of satisfaction with PrEP-related health care services received. Data are collected using a Likert scale.	Attkisson & Greenfield, 2004		X	X	
Satisfaction with Interpersonal	For participants randomized to PN intervention only; 9-item measure of satisfaction with care provided by a patient navigator. Data are collected using a Likert scale.	Jean-Pierre et al., 2012		X	X	

Relationship with Navigator						
PN Intervention Acceptability	For participants randomized to PN, brief telephone key informant interview assessing acceptability of the PN intervention. Data are qualitative.	Team developed			X	
PrEP Initiation	Up to 10 survey items assessing whether patient had received a prescription for PrEP, decided to fill a PrEP prescription, and taken at least one dose of PrEP since the start of the study. Categorical data are collected.	Team developed	X	X	X	
Demographic Characteristics	Demographic items (e.g., age, race, gender, sexual orientation, relationship status, country of origin, U.S. citizen status, primary language, education level, employment status, income, health insurance status) have categorical response options. Age data are collected with numeric text entry.		X			
Medical Characteristics	Comorbid medical conditions, medications prescribed, history of STI testing					X

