PrEP-Related Health Care Received	Date(s) appointment scheduled for PrEP consultation; Date attended appointment for PrEP consultation; Date(s) health care provider wrote PrEP prescription(s); Date the first follow-up PrEP appointment(s) scheduled; Date(s) of follow-up medical appointment attended; Data recorded in EHR regarding adherence and discontinuation; other data regarding PrEP-related health care	Team developed				X

Abbreviations: BL = baseline; 3m = 3 month follow/up appointment; 6m = 6 month follow-up appointment; EHR = electronic health record; STI= sexually transmitted infection; PN = patient navigation

**MEMS Device Data Collection.** At baseline and 3-month follow-up, all participants will be asked if they have obtained a prescription for PrEP. Those who indicate that they have been prescribed PrEP and have taken at least one pill will be asked to track their PrEP adherence via a Medication Event Monitoring System (MEMS) device. A MEMS device is a standard prescription bottle that includes a larger lid containing a MEMS monitoring cap. During the baseline or at a 3-month follow-up visit, the research coordinator will give participants a MEMS device with instructions for its use. Participants will be instructed to place all PrEP pills into a MEMS container so when a pill is removed, the device will record date and time of removal of the medication dose using a small microcircuit. A medication “event” is removal of bottle closure, followed by replacement of closure. A study staff member will collect MEMS devices from participants in-person at the 3- and/or 6- month follow-up and connect them to a MEMS® Reader, which transfers data to a secured server via a secured web platform. Timing adherence will be calculated as percentage of time each participant took PrEP as prescribed by determining number of doses of PrEP taken at 24-hour intervals for a once daily PrEP regimen and dividing it by number of days adherence was monitored with MEMS.

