To test the preliminary impact of the intervention, a series of logistic regression models will be conducted, with each of the 6 binary PrEP continuum primary outcome variables set as a criterion: 1) appointment scheduled for PrEP consultation; 2) appointment attended for PrEP consultation; 3) PrEP prescription received; 4) PrEP prescription filled; 5) PrEP initiated; and 6) PrEP follow-up medical appointment attended. In addition, we hypothesize that receipt of the PN intervention will be associated with increased self-reported PrEP adherence over the past seven days (also a primary outcome variable). To test the preliminary impact on the two measures of self-reported PrEP adherence, we will conduct two linear regression analyses with intervention group assignment entered as the independent variable and each measure of PrEP adherence entered as the dependent variable. Potential demographic variables (e.g., age) will be assessed for inclusion in the models as well. Finally, linear mixed models will be conducted to examine changes in 1) barriers to PrEP-related care; 2) PrEP knowledge, 3) PrEP efficacy beliefs; 4) medication beliefs, 5) PrEP attitudes; and 6) medication self-efficacy. Linear mixed models allow us to account for the dependence of the repeated measures. Different covariance structures will be implemented and the information criterion such as AIC or BIC will be used for model selection. We hypothesize that participants randomized to PN will have greater engagement in PrEP continuum behaviors compared to participants randomized to UC. Since data analyses are exploratory, and there is not adequate statistical power to evaluate efficacy of the PN intervention, these tests can only provide information regarding data trends and effect sizes. If the study and PN intervention methods are found to be feasible and acceptable, a larger study with adequate statistical power will be conducted to appropriately evaluate the efficacy of the PN intervention.

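### Current PrEP users are eligible, but PrEP use at baseline is neither a stratification factor nor a named covariate, so the pilot's effect sizes lose precision and interpretability

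*Combined protocol and SAP*

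**What the plan says.** - **Who enters.** Inclusion/Exclusion Criteria: "Participants who previously were prescribed or are currently taking PrEP will be included in the study". No cap or quota on users is given.
- **How they are allocated.** The opening summary says that staff will "individually randomize each participant to 1 of 2 conditions: usual care plus written information (UC) or PN". The Randomization section describes a "blocked randomization sequence (in blocks of 4 participants) to balance randomization across the arms of the study". It names no stratification factor; that the list is unstratified is inferred from this silence.
- **What is known at that moment.** Randomization takes place "immediately following the baseline survey data collection". Table 1 lists the 7-day PrEP adherence items and the PrEP initiation items at baseline. The MEMS paragraph adds: "At baseline and 3-month follow-up, all participants will be asked if they have obtained a prescription for PrEP". That question concerns a prescription, and a follow-on concerns having taken a pill, so the 7-day items in Table 1 are the better source for current use.
- **How outcomes are modelled.** The Statistical Analysis Plan uses logistic regression for six binary continuum outcomes and linear regression for two adherence measures. On covariates it says only: "Potential demographic variables (e.g., age) will be assessed for inclusion in the models as well". It mentions neither baseline PrEP use nor an analysis by baseline use.
- **What the estimates are for.** The same section calls the analyses exploratory and inadequately powered, and says they inform only on trends and effect sizes.

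**The concern.** Blocks of 4 equalise the head count per arm and nothing else. The eligibility rule brings together two groups whose expected outcomes probably differ widely. Table 1 measures initiation partly by whether the participant has "taken at least one dose of PrEP since the start of the study", which a continuing user meets almost automatically. Prescription received, prescription filled and follow-up visit attended are also likely to be commoner in people already on PrEP.

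If one arm happens to receive several more users, the unadjusted comparison on these outcomes moves for a reason unrelated to navigation. Effect sizes are what the plan says its tests can provide, and they come from about 30 people per arm, so one realised estimate could be hard to read.

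**Working it through.** **Inputs from the documents.** N = 60 (opening summary: "Bilingual research assistants will recruit 60 young adult Latino MSM at-risk for HIV in San Diego County, California"); two arms; blocks of 4, so 60/4 = 15 blocks. The allocation ratio is not stated; 1:1, or 30 per arm, is inferred from blocks meant to balance the arms. There is no figure of the plan's own to reproduce: the 60 rests on general recommendations for pilot trials, without alpha, power or effect size.

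**Assumptions, not in the documents.** K current users among the 60; the outcome gap between users and others; no navigation effect; no dropout.

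**Step 1. Chance of imbalance.** The number of users in one arm is X ~ Hypergeometric(60, K, 30), and the difference between arms is d = 2X − K.

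| K | Event | Probability |
|---|---|---|
| 12 | difference of 4 or more (8 v 4) | 0.333 |
| 15 | difference of 5 or more (10 v 5) | 0.233 |
| 15 | difference of 7 or more (11 v 4) | 0.072 |
| 18 | difference of 6 or more (12 v 6) | 0.158 |

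Simulating 15 blocks of 4 gave 0.334, 0.231, 0.072 and 0.158. These are two-sided; at K = 15, about 0.233/2 = 12% have 5 or more extra users in the navigation arm.

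**Step 2. Shift in the risk difference.** Shift = (d/30) × gap. With d = 5 and a gap of 75 points (100% v 25%): 5/30 × 75 = 12.5 points. With a gap of 30 points: 5/30 × 30 = 5.0 points.

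Over a wider range, in percentage points:

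| Users of 60 | SD of difference in user share | SD of shift, gap 30 | 95th percentile of absolute shift, gap 30 | SD of shift, gap 70 | 95th percentile of absolute shift, gap 70 |
|---|---|---|---|---|---|
| 6 | 7.8 | 2.3 | 4.0 | 5.5 | 9.3 |
| 12 | 10.4 | 3.1 | 6.0 | 7.3 | 14.0 |
| 18 | 11.9 | 3.6 | 6.0 | 8.4 | 14.0 |
| 24 | 12.8 | 3.8 | 8.0 | 9.0 | 18.7 |
| 30 | 13.0 | 3.9 | 8.0 | 9.1 | 18.7 |

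**Step 3. Set against the unadjusted standard error.** With 15 of 60 users and rates of 100% and 25%, the overall rate is 0.25 × 1 + 0.75 × 0.25 = 0.4375. The SE is √(2 × 0.4375 × 0.5625/30) = 12.8 points. The 12.5-point shift is about one SE, and it is part of that SE, not an addition to it.

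**Step 4. What adjustment recovers.** The average within-group variance is 0.25 × 0 + 0.75 × (0.25 × 0.75) = 0.1406. The adjusted SE is about √(2 × 0.1406/30) = 9.7 points, and the variance ratio is 0.1406/0.2461 = 0.57, a 43% cut. With rates of 90% and 20% and 12 to 24 users, the cut is 35% to 47%; with 90% and 40% it is 16% to 25%. All this is on the risk-difference scale.

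**Step 5. What stratified blocks add once the model adjusts.** The effective size is the sum over strata of n₁n₀/(n₁ + n₀).

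- Users 10 v 5, others 20 v 25: 50/15 + 500/45 = 14.44, against 15 if balanced. SE inflation is √(15/14.44) = 1.019.
- Users 12 v 6, others 18 v 24: 4 + 10.29 = 14.29; inflation 1.025.
- Users 8 v 4, others 22 v 26: 2.67 + 11.92 = 14.58; inflation 1.014.

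After adjustment, even these uneven splits cost only about 1.4% to 2.5% in SE.

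**The case against.** The strongest reply is that simple permuted blocks are a legitimate design, that chance imbalance is what the standard error measures, and that this is a pilot whose main aims are feasibility and acceptability. Most of that stands. Nothing in the plan is invalid on this point, and the size rests on a user share and an outcome gap that the documents do not give.

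A reader might draw three stronger conclusions that the documents do not support.

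- *That the design is biased.* It is not. Allocation is random and concealed; over repeated trials the imbalance averages to zero.
- *That an imbalance could not be repaired after the fact.* It could. PrEP adherence and initiation items are collected at baseline, so results can be adjusted for or tabulated by baseline use. The SAP also plans to describe both groups on outcomes measured at baseline, so an imbalance in those measures should be visible.
- *That all the primary outcomes would move together.* This is not established. The plan does not say how people not taking PrEP are scored on adherence; if they are left out, the formula in step 2 does not apply to it. Nor does it say whether a person already on PrEP counts as having scheduled or attended a PrEP consultation.

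The pilot label does not dispose of the point. Effect sizes are what the tests are said to deliver, and no planned model allows for the factor most likely to blur them.

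**Conclusion.** The point holds as a loss of precision and interpretability. The likely strongest predictor of the continuum outcomes can be measured before allocation, but the plan neither balances it nor names it for adjustment. With a wide gap between users and others, a quite ordinary imbalance moves an unadjusted estimate by about its own standard error. With few users, or a gap near 30 points, the effect is only a few points.

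The main remedy lies in the analysis. Stratified allocation is a useful but minor addition, because adjustment captures nearly all the gain. The probabilities assume 30 per arm and no dropout; the shifts also depend on the assumed user share and outcome rates.

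**What to change.** **In the Statistical Analysis Plan:**

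1. Define current PrEP use at baseline from the baseline survey, for example from the 7-day adherence items in Table 1.
2. Include it as a prespecified covariate in every continuum outcome model, whatever the check on demographic variables shows.
3. Because nearly all users may have some of the outcomes, use a method that tolerates near-complete separation, such as Firth logistic regression or a stratum-weighted risk difference.
4. Tabulate each continuum outcome by arm and baseline use.

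**In the Randomization section,** if the application supports it (the documents do not say), run separate blocks of 4 for current users and others. The imbalance is then at most 2 users, or 2/30 = 6.7 points of user share, and the shift at a 70-point gap is at most 4.7 points.

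**Cost.** The analysis change needs a few lines of text and no new data. An adjusted odds ratio is not the same quantity as an unadjusted one, so the plan should say which it reports. Stratification needs the status entered before the application is opened and can leave two incomplete blocks, so the arms could end at 32 v 28 at worst.
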